7.12 Analysis of Exploratory Endpoint(s)

There are no exploratory endpoints for this study.

CONFIDENTIAL AND PROPRIETARY

This document contains information that is confidential and proprietary to Smith & Nephew PLC and Smith & Nephew, Inc. and is intended for use only by Smith+Nephew and its manufacturer. It shall not be reproduced or copied in whole or in part, nor shall the contents be disclosed by any means without prior written permission from Smith+Nephew, nor shall anyone make any use of it that is contrary to the expressed or implied wishes of Smith+Nephew.

Statistical Analysis Plan

Post-Approval Study of the R3™ Biolox® delta Ceramic Acetabular System – United States

Number: 16-4565-10
ST: 1176
Version: 5.2, 19-JAN-2024
Page: 19 of 22

7.13 Analysis of Safety Endpoint(s)

The number of AEs, SAEs, USADEs, Reoperation and Revisions, and the number and the percentage of patients experiencing AEs, SAEs, USADEs will be presented for the enrolled set.

The number of AEs and the number and the percentage of patients with at least one AE will be presented for AEs and SAEs.

The number and the percentage of patients with at least one AE will be presented by severity, seriousness, device relatedness and procedure relatedness.

Adverse event definitions are shown below and are as per the study protocol.

7.13.1 Adverse Event (AE)

An AE is any untoward medical occurrence, unintended disease or injury, or untoward clinical signs (including abnormal laboratory findings) in subjects, users, or other persons, whether or not related to the study medical device.

This definition includes but is not limited to:

- events related to the study device
- events related to the procedures involved

7.13.2 Serious Adverse Event (SAE)

A SAE is an adverse event that:

- resulted in death,
- was life threatening (at the time of the event); or
- resulted in hospitalization (initial or prolonged); or
- resulted in a disability or permanent damage (a significant, persistent, or permanent change, impairment, damage or disruption in the patient's body function/structure, physical activities and/or quality of life); or
- resulted in a congenital anomaly or birth defect; or
- required medical or surgical intervention to preclude permanent impairment of a body function or prevent permanent damage to a body structure; or
- does not fit the other outcomes above but may jeopardize the subject and may require medical or surgical intervention (treatment) to prevent one of the other outcomes.

Planned hospitalization for a pre-existing condition, or a procedure required by the protocol, without serious deterioration in health, is not considered a serious adverse event.

CONFIDENTIAL AND PROPRIETARY

This document contains information that is confidential and proprietary to Smith & Nephew PLC and Smith & Nephew, Inc. and is intended for use only by Smith+Nephew and its manufacturer. It shall not be reproduced or copied in whole or in part, nor shall the contents be disclosed by any means without prior written permission from Smith+Nephew, nor shall anyone make any use of it that is contrary to the expressed or implied wishes of Smith+Nephew.

Statistical Analysis Plan

Post-Approval Study of the R3™ Biolox® delta Ceramic Acetabular System – United States

Number: 16-4565-10
ST: 1176
Version: 5.2, 19-JAN-2024
Page: 20 of 22

7.13.3 Adverse Device Effect (ADE)

An ADE is an adverse event related to the use of an investigational medical device.

This definition includes:

- adverse events resulting from insufficient or inadequate instructions for use, deployment, implantation, installation, or operation, or any malfunction of the investigational medical device
- any event resulting from use error or from intentional misuse of the investigational medical device.

7.13.4 Serious Adverse Device Effect (SADE)

A SADE is an adverse device effect that has resulted in any of the consequences characteristic of a serious adverse event.

7.13.5 Unanticipated Serious Adverse Device Effect (USADE)

Any serious adverse effect on health or safety or any life-threatening problem or death caused by, or associated with, a device, if that effect, problem, or death was not previously identified in nature, severity, or degree of incidence in the investigational plan or application (including a supplementary plan or application), or any other unanticipated serious problem associated with the device that relates to the rights, safety, or welfare of subjects.

7.13.6 Device Deficiency

A device deficiency is an inadequacy of a medical device with respect to its identity, quality, durability, reliability, safety, or performance. Device deficiencies include malfunctions, use errors, and inadequate labelling.

7.13.7 Assessment of Adverse Event Severity

The Investigator will assess and categorize AEs as mild, moderate, or severe based on the following definitions:

- Mild: the subject is aware of the sign or symptom, but finds it easily tolerated. The event is of little concern to the subject and/or little clinical significance. The event is not expected to have any effect on the subject's overall health or well-being.

CONFIDENTIAL AND PROPRIETARY

This document contains information that is confidential and proprietary to Smith & Nephew PLC and Smith & Nephew, Inc. and is intended for use only by Smith+Nephew and its manufacturer. It shall not be reproduced or copied in whole or in part, nor shall the contents be disclosed by any means without prior written permission from Smith+Nephew, nor shall anyone make any use of it that is contrary to the expressed or implied wishes of Smith+Nephew.

Statistical Analysis Plan

Post-Approval Study of the R3™ Biolox® delta Ceramic Acetabular System – United States

Number: 16-4565-10
ST: 1176
Version: 5.2, 19-JAN-2024
Page: 21 of 22

- Moderate: the subject has discomfort enough to cause interference with or change in usual activities. The event is of some concern to the subject's health or wellbeing and may require medical intervention and/or close follow-up.
- Severe: the adverse event interferes considerably with the subject's usual activities. The event is of definite concern to the subject and/or poses substantial risk to the subject's health or well-being. The event is likely to require medical intervention and/or close follow-up and may be incapacitating or life threatening. Hospitalization and treatment may be required.

7.13.8 Assessment of Adverse Event Relationship to Device and Procedure

All adverse events (AE) are assessed for relatedness to the study device and study procedure based upon the following definitions:

- Unrelated: the event is clearly not related to the study device or study procedure
- Possible: the event may or may not be related to the study device or study procedure. A relationship cannot be ruled out.
- Definite: the event is clearly related to the study device or study procedure.

7.14 Other Data Summaries

Subgroup analyses of the primary endpoint based upon race will be conducted. Descriptive summaries of these analyses, for each racial subgroup, will be provided.

Due to the COVID-19 pandemic, it is expected that restrictions on in-office visits may cause out of window in-office follow-up visits and result in missing or out of window data such as mHHS and radiographic endpoints. To evaluate whether there is a significant difference in the mean mHHS for subjects who use the patient portion of mHHS and the mean for subjects who use the overall mHHS, the following additional analysis will be performed:

- A comparison of total mHHS scores (including RoM assessments) from subjects who completed an in-person visit compared to scores from subjects who completed the telephone visit at the 3-year follow-up visit. This will be tested using an independent sample t-test.

Radiographic Findings

CONFIDENTIAL AND PROPRIETARY

This document contains information that is confidential and proprietary to Smith & Nephew PLC and Smith & Nephew, Inc. and is intended for use only by Smith+Nephew and its manufacturer. It shall not be reproduced or copied in whole or in part, nor shall the contents be disclosed by any means without prior written permission from Smith+Nephew, nor shall anyone make any use of it that is contrary to the expressed or implied wishes of Smith+Nephew.

Statistical Analysis Plan

Post-Approval Study of the R3™ Biolox® delta Ceramic Acetabular System – United States

Number: 16-4565-10
ST: 1176
Version: 5.2, 19-JAN-2024
Page: 22 of 22

At the 3 year postoperative endpoint, the frequency of subjects will be tabulated for mHHS pain component by whether subjects show a >4 degree change in acetabular cup inclination angle from baseline. The relationship between whether subjects showed pain as "Mild", "Moderate", "Marked" or "Disabled" (from mHHS pain score) and those with a greater than 4 degree change in acetabular cup angle inclination from baseline will be compared using Fisher's Exact test.

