3.2.4 Telephone Follow-Up

If subjects are unable to return for follow-up visits to the Investigator's office, they may be contacted by telephone to assess their status. Subjects will be asked whether the device is in place or has been revised and asked whether any adverse events related to the study hip device have occurred since the last visit.

In addition, the patient portion of mHHS (all data except for Range of Motion (ROM), Trendelenburg and Leg Length Difference) will be collected during this Telephone Follow-Up Assessment^{1,2}. Note that if the subject later returns for a follow-up visit to the Investigator's office during the same interval as a telephone follow-up visit, the complete mHHS will be collected and included in the analyses in lieu of the patient portion.

The proposal to collect the patient portion of the mHHS data by telephone interview, and to use these data in lieu of the full mHHS when necessary, is justified based on the clinical study that has been published in the Journal of Telemedicine and Telecare in 2005² which confirms that there is overall no statistical difference between in-office complete mHHS and telephone patient portion mHHS assessments. Note that 'mHHS' in this study refers to a modification in how the "distance walked" question is asked, to make it more relevant for the European study population. However, in the article², 'mHSS' refers to the patient portion of the HHS without ROM, Trendelenburg and Leg Length Difference, as these cannot be collected remotely. Removal of the ROM and deformity components gives a maximum score of 91, which is multiplied by a factor of 1.1 in order to derive a total score out of 100. The published study showed that the differences between the complete HHS and the patient portion of the HHS are not statistically significant or clinically relevant, and thus the patient portion can be used for routine follow-up assessment of patients who have undergone total hip replacement².

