5 STUDY ENDPOINTS

5.1 Primary Endpoint(s)

The primary endpoint is overall study success at 3 years postoperative. Success is defined the same way it was in the PMA cohort, to allow comparison. The primary endpoint will be analyzed using the exact binomial test. Overall success is defined as:

- No component revision,
- Modified Harris Hip Score (mHHS) of at least 80 points, and
- No radiographic failure, defined as:

No radiolucencies greater than 2 mm in 50% or more in any of the cup or stem zones, no femoral or acetabular subsidence greater than or equal to 5 mm from baseline, and no acetabular cup inclination changes greater than 4 degrees from baseline when accompanied by "Mild", "Moderate", "Marked" or "Disabled" mHHS pain score.

In the event that the need for remote visits due to COVID-19 significantly impacts the primary endpoint, the following additional analyses will be performed to allow inclusion of as many study subjects as possible in the analysis:

- (1) An alternative analysis in which overall success will consist of components that can be remotely collected via telephone, and will be defined as:
 - No component revision,
 - Patient portion of the Modified Harris Hip Score (mHHS), as described in Section 3.2.4**Error! Reference source not found.**, of at least 80 points.
- (2) An alternative analysis that allows for post-three-year data to be used in place of missing or incomplete three-year visits ("rollback").

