7.3 Handling of Missing, Incomplete and Repeat Data

When data are being summarized, only the non-missing values will be evaluated for computing summary statistics.

In general, partial dates will be imputed as follows:

- if only the day is missing, the first day of the month will be assumed;
- if the day and the month are missing, January 1st will be assumed;
- if a date is completely missing or unknown and the visit is not indicated on the CRF, the data will not be included in a specific time window for analysis. Note that all AEs will be included regardless of whether the date is missing or incomplete.

When subjects do not attend an in-office study visit and a telephone visit is conducted instead, the data from telephone visit will be used for analyses wherever possible.

When the patient misses the final (3 year) visit but is able to return the office at a later date, the additional mHHS and radiographic data that were not collected during the telephone visit will be collected and used for the final analyses at 3 years.

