Due to subject visit restrictions associated with COVID-19 pandemic, it is expected that Protocol Deviations will occur that may affect the subject accountability rates. In particular, radiographic data and data that can only be collected at the office follow up are likely to be missing or out of window. However, the telephone survey will ensure that most of the key information needed for the primary analysis at the 3-year follow-up visit is collected. Additionally, every effort will be made to gather radiographic data and the complete HHS at a later time when an in-person visit was not completed within the 3-year window.

To present a thorough assessment of hip accountability, the following information will be included in the annual reports and final study report:

- (1) The typical accountability table that has been presented in each annual report will be presented, using the same rules for inclusion in each category (i.e. Actual^A, Actual^{Awithinwindow}, Actual^B, Actual^{Mod. B}).

CONFIDENTIAL AND PROPRIETARY

This document contains information that is confidential and proprietary to Smith & Nephew PLC and Smith & Nephew, Inc. and is intended for use only by Smith+Nephew and its manufacturer. It shall not be reproduced or copied in whole or in part, nor shall the contents be disclosed by any means without prior written permission from Smith+Nephew, nor shall anyone make any use of it that is contrary to the expressed or implied wishes of Smith+Nephew.

Statistical Analysis Plan

Post-Approval Study of the R3™ Biolox® delta Ceramic Acetabular System – United States

Number: 16-4565-10
ST: 1176
Version: 5.2, 19-JAN-2024
Page: 17 of 22

- (2) Final 3-year accountability, which will include telephone visit data (or full HHS if available) plus out-of-window radiographic data as allowable for "complete data" (Actual^Awithinwindow, and Actual^A), and telephone visit data alone as allowable for other accountability categories including Actual^B and Actual^{Mod. B}.
- (3) A listing of deviations and missed/out of window visits that result from the COVID-19 pandemic.

Screening failures and patients discontinued from the study prematurely will be presented with a breakdown of the reasons for discontinuation as reported in the CRF.

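### The SAP's only in-study check of the telephone hip score against the full score compares means in different subjects, and does not show how often the score version changes success at 80 points

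*SAP*

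**What the plan says.** SAP 3.2.4 allows the patient portion of the mHHS, without range of motion, Trendelenburg and leg length difference, to be collected by telephone and used when the full score is not available. The support offered is a published study, which the SAP describes as finding no statistically significant or clinically relevant difference between the two. The scaling appears in that description: "Removal of the ROM and deformity components gives a maximum score of 91, which is multiplied by a factor of 1.1".

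Full scores take precedence. If the subject attends in the same interval, "the complete mHHS will be collected and included in the analyses in lieu of the patient portion" (SAP 3.2.4). If the subject misses the 3-year visit and returns later, "the additional mHHS and radiographic data that were not collected during the telephone visit will be collected and used for the final analyses" (SAP 7.3). SAP 7.3 also says that telephone data feed the analyses as far as they can.

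The primary endpoint needs an mHHS of at least 80 (SAP 5.1 and 7.10). Alternative analysis (1) in SAP 5.1 applies the same cut to the patient portion and drops the radiographic component. It is conditional: "In the event that the need for remote visits due to COVID-19 significantly impacts the primary endpoint".

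The only planned comparison of the two score versions is in SAP 7.14. Scores from in-person subjects are "compared to scores from subjects who completed the telephone visit at the 3-year follow-up visit", and "This will be tested using an independent sample t-test". No decision rule is attached.

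**The concern.** There are two separate problems.

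- **Different people.** The test contrasts in-person attenders with telephone attenders. Any difference in means combines the effect of score version with any difference between those who could and could not come. The two could cancel, or patient mix alone could produce a difference. The SAP attributes missed visits to COVID-19 restrictions, so the mixing may be small, but the test cannot show its size. Failure to find a difference would not be evidence of agreement.
- **Means, not classification.** The score enters the endpoint only through the cut at 80. Equal means are compatible with individual subjects crossing the cut in either direction.

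The question that matters for the endpoint, and for alternative analysis (1), is how often the score version changes success. The planned check does not answer it, although every complete in-person form already contains the items needed for both scores.

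**Working it through.** **Inputs.** Cut of 80 points (SAP 5.1, 7.10). Patient-portion maximum 91 and factor 1.1 (SAP 3.2.4, given there for the cited article; assumed here to be the scaling applied in this study). The omitted items are inferred to carry 100 − 91 = 9 points. The CRF is not shown, so this range is an assumption.

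**Notation.** P = raw patient portion; R = points on the omitted examination items (0 to 9).

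**The SAP's scaling.** 91 × 1.1 = 100.1, in line with the SAP's description of a score out of about 100.

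**Pass rules.**
- Telephone: 1.1 × P ≥ 80, so P ≥ 80/1.1 = 72.73.
- Full score: P + R ≥ 80, so P ≥ 80 − R.

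**When they disagree.** The two thresholds coincide only at R = 80 − 72.73 = 7.27.
- R below 7.27: telephone passes and full score fails for P from 72.73 up to, but not including, 80 − R.
- R above 7.27: telephone fails and full score passes for P from 80 − R up to, but not including, 72.73.

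These inequalities do not depend on whole-number scoring.

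**One example each way.**

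| P | R | Rescaled, 1.1 × P | Full, P + R |
|---|---|---|---|
| 75 | 4 | 82.5 (pass) | 79 (fail) |
| 72 | 8 | 79.2 (fail) | 80 (pass) |

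The same-form difference is 1.1P − (P + R) = 0.1P − R. Its average can be near zero while individual values are not, which is why a comparison of means does not settle classification.

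**How much one subject can matter.** The plan's figure first: the null rate is 0.864 − 0.08 = 0.784. At the planned minimum of 146 evaluable subjects, the one-sided exact binomial test rejects from 123 successes, with exact alpha 0.0492 and power 0.8125 at 0.864, so 146 reproduces. With 122 successes the p-value is 0.075. One reclassified subject therefore changes the conclusion only if the count lies at that boundary. Nothing in the documents says that it will.

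**What cannot be computed.** The documents give no distribution of P or R and no number of telephone-only subjects, so the rate of disagreement cannot be derived from them.

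**The case against.** The strongest reply is that SAP 7.14 sets out to compare means and that an independent t-test does that. The check is supplementary and carries no decision rule, and the SAP rests the substitution on a published study. All of this stands, and there is no contradiction or wrong figure here. It does not remove the point: the sponsor chose to add an in-study check, and a more informative one is available from data already collected.

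The route to the primary result is also narrow. Success needs radiographic status, SAP 7.10 analyses subjects with evaluable 3-year data, and a subject who returns for a radiograph is planned to supply the missing mHHS items too. This stands and limits the weight of the point. What remains is the general provision in SAP 7.3 for using telephone data, and the conditional alternative analysis.

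A reader might infer from SAP 7.6 that telephone scores widely enter the primary analysis, since final accountability is one "which will include telephone visit data (or full HHS if available) plus out-of-window radiographic data as allowable for" complete data. That text defines accountability categories, not the analysis set, and does not support the inference. Nor do the documents expressly adopt the factor 1.1 for this study: it appears in the account of the cited article and is not restated in SAP 7.14.

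Finally, a same-form comparison contains no telephone data. It tests item omission and rescaling, not the effect of asking by telephone. That is a real limit of the remedy.

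**Conclusion.** The point holds as a minor suggestion. The planned t-test mixes score version with attendance, cannot establish agreement, and does not examine pass or fail at 80.

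If the described scaling is the one used and the omitted items carry up to 9 points, the two versions can classify the same subject differently in both directions. How often this happens is unknown. A reader might infer that telephone scoring inflates the success rate, or that the primary result is compromised. The documents support neither: they give no score distribution from which a direction or size of bias could follow, and they plan for full scores to replace telephone scores where these are obtained. The sample size and the primary test are unaffected.

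**What to change.** In SAP 7.14:

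1. For all subjects with a complete in-person 3-year mHHS, compute the full score and the rescaled patient portion from the same form. Report the paired mean difference with 95% CI, the limits of agreement, and the 2x2 table at 80 points with the discordance rate and its exact 95% CI.
2. State the scaling factor used in this study.
3. Keep the in-person versus telephone comparison as descriptive only.
4. If any subject in the primary analysis is scored by telephone only, list these subjects. Identify those whose classification could change over the possible range of the omitted items, and repeat the exact binomial test with them classified both ways. Work from that range for each subject, not from a fixed score band.

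**Cost.** Some SAP wording and one extra table; step 4 applies only if such subjects exist. No new visits are needed, provided that the mHHS items are stored separately. The protocol synopsis puts the end of data collection at May 2023 and SAP 5.2 is dated January 2024, so the table would be an addition after data collection and should be labelled as such. It would not test telephone mode.
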